Feasibility Testing (Aim 1): We will demonstrate feasibility, acceptability, and validity of the SPEEKO for Elderspeak feedback app use by staff in the NH and identify needed modifications prior to testing in Aim 2. The PI worked with the Speeko Company (see resources and letter) to develop the elderspeak feedback app. App proof of concept has been

demonstrated in the lab setting. With a preliminarily trained natural language processing detection model, diminutive accuracy testing resulted in a sensitivity (true positive rate) of 87.7% and a specificity (true negative rate) of 99.9%. The app provides immediate feedback with potential to increase CHATO effects. Recordings are analyzed by a natural language processing app that provides immediate and private feedback and encouragement to individual staff. The app detects common elderspeak terms of endearment (diminutives), identified through reanalysis of the PI's archived NH recordings.⁵⁶ Detection algorithms were also developed using the recordings to establish proof of concept. App modifications were completed to enhance recording quality and transcription accuracy and to filter noise.

Further feasibility and detection model algorithm optimization will be tested at Garden Terrace of Overland Park, a NH dedicated to dementia care. A detailed protocol and user manual will be developed, and pilot tested. Feasibility will be tested with five CNA volunteers (n=5) who will each record a 2-hour care session. These staff will record their speech during a 2-hour work session to demonstrate use of the feedback app and complete a 10-item usability scale. Potential issues (e.g., background noise, Internet and bandwidth adequacy, acceptability to residents) will be assessed. App outputs will be compared to data from transcription and psycholinguistic coding, using our established protocols, to validate app reliability for diminutive detection. The CNAs will be interviewed about use of the app, providing additional data to improve the system for Aim 2 testing. If validated, app functions may be expanded to monitor additional aspects of elderspeak (i.e., "we" pronoun substitutions).

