Recording equipment: To create high fidelity recordings for optimal natural language processing, each CNA volunteer will wear a hypercardioid condenser headset microphone with unidirectional sound sensitivity. This microphone assembly is designed to pick up sound directly in front of the microphone and to reject off-axis background sounds such as from residents and staff. In addition to using microphone hardware to isolate the user's voice, the app uses digital noise gating and frequency level stabilization to limit extraneous content and to support audio quality. An iPod Touch with password encryption will be carried in the pocket of the CNA volunteer. The iPod Touch will be connected to the microphone by a standard 3.5 mm headphone jack. The battery life of the iPod Touch enables continuous use during the 2-hour recording window for each CNA.

iOS App: The iPod Touch will run an iOS app that records and processes audio in real time and utilizes voice activation frequency technology to isolate and record when a user is speaking and discard periods of silence from the recording analysis. Original back-up recordings are saved locally on the secured iPod Touch for the Project Director to access through a master password within the app to all user accounts. Together, the iPod Touch and low profile, lightweight headset microphone will provide high quality audio for maximal analytic accuracy and minimal workflow interruption or reaction by residents and staff. The initial 15 minutes of each recording session will be discarded to allow CNAs time to adjust to being recorded. Recordings will be analyzed in real time using a transcription detection model powered by Amazon Transcribe. All speech-related data are communicated using Transport Layer Security protocols to ensure end-to-end security and HIPAA compliance. Transcripts will be downloaded to the iPod Touch app that identifies and tabulates diminutives, displaying a feedback infographic at the end of the session.

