Audio recording supports precise measurement of verbal communication including duration, intensity, and patterns and is less invasive than videotaping, encouraging natural communication and maintaining privacy. Recordings can be reviewed repeatedly to verify accuracy and reliability. Limitations are (1) alteration of natural speech and behavior due to the awareness of recording and (2) inability to control for environmental factors such as noise. Research has established that NH staff do not significantly modify communication if recording is presented in a nonjudgmental manner^{60,61} and this was confirmed in the PI's

research.⁴³ The audio recording protocol is designed to measure communication in NHs⁶² and health care settings;⁶³ it was effective in the PIs research, uses measures to limit the Hawthorne effect (i.e., minimally obtrusive recording equipment), and will record each CNA during the same time periods from day to day to assure consistency.^{8,27,42-44,64,65}

Preliminary Effects Testing (Aims 2): We will test preliminary effects of app feedback on elderspeak use in audio-recorded staff communication. A cluster randomized trial will be conducted in six NHs that participate in CHATO training. We will compare the immediate and delayed-feedback control groups on elderspeak (diminutive) changes after participation in CHATO. We hypothesize that staff who receive immediate feedback will demonstrate greater reductions in use of diminutives, the most common and recognizable marker of elderspeak, compared to control group staff before they receive delayed feedback. We will validate app accuracy by comparing app results to psycholinguistic coding using our established protocols for data reduction, transcription, and coding.^{8,44,66}

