Data Archiving. After each recording session, the Project Director will screen and edit recordings to delete any resident or other staff communication or other identifiers (names) so that the archived recording contains only the desired CNA participant's voice. Recordings and data will be archived in a dedicated research computer labeled with unique identifier codes. To reduce the Hawthorne effect, the initial 15 minutes of each recording session will be discarded. An estimated hour of recorded speech will be collected four times for each of

60 CNAs, providing approximately 240 hours of recordings for transcription, coding, analysis, and additional app algorithm training.

Psycholinguistic Coding. RAs will transcribe all recordings (for both groups) and will use brackets to code diminutives using our established operational definitions and protocols.^{10,43,45,56,78} To assure reliability, as used in our past studies, RAs will be trained on a practice sample until achieving 90% agreement for utterance segmentation and coding. A second trained coder will independently code 10% of the actual study transcripts. Additional training will be provided if agreement falls below 85%. Systematic Analysis of Language Transcripts (SALT)⁷⁹ will be used to tabulate frequencies for each code. Data will be entered in an electronic spreadsheet using unique identifier codes and stored on a secure computer. RAs will not have access to the key connecting codes with identifying information and will be blind to group assignment and assessment time points.

Acceptability and Cost Testing (Aim 3): CNAs testing the app will complete the System Usability Scale (SUS), a validated 10-item industry standard survey to rate (1) use of the microphone, recorder, and app; (2) acceptability and work compatibility; (3) feedback infographic; and (4) interest in self-monitoring. We hypothesize that staff who use the app will find it acceptable and beneficial for their practice. As in our prior studies, we will use process-based costing to determine average costs for using the SPEEKO for Elderspeak feedback app, comparing costs relative to any difference determined for reductions in diminutive use in the immediate and delayed feedback groups.^{80,81} Evaluation of acceptability and costs are key factors in consideration of ongoing plans for app dissemination in NHs and across other long-term services and support settings.

C. Sample size, statistical methods, and power calculation

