Aim 1: We will demonstrate feasibility, acceptability, and validity of the SPEEKO for Elderspeak feedback app with detection model algorithm optimization with a diminutive accuracy testing benchmark of 80% or higher. App outputs will be compared to data from transcription and psycholinguistic coding, using our established protocols, to validate app reliability for diminutive detection. Also, an analysis of a CNA-completed, 10-item usability scale (The System Usability Scale) with an acceptability benchmark of 50% or higher.

Aim 2: Linear Mixed Models (LMMs) or Generalized LMMs, depending on the distribution of each outcome, will be developed to determine the impact of group assignment (feedback or no feedback) on use of elderspeak diminutives. Baseline diminutive use, group (feedback vs. no feedback), recording session (pre- and post CHAT sessions 1, 2, and 3), and interaction between intervention and session will be fitted as fixed effects. To account for clustering, each NH will be fitted as a random effect. To account for correlation due to repeated measurements, an appropriate covariance pattern will be determined from data. CNA and resident sex and CNA knowledge gain will be tested as covariates. Aim 2 will estimate variability, effect sizes, and intracluster correlation for a future larger-scale study. Sample sizes of as few as 30 in each group, or 10 CNAs on average in each NH, will achieve 80% power to detect a difference between the group means of 0.74 to 0.76 standard deviations, assuming the intracluster correlation coefficient ranging from 0.001 to 0.01 and coefficient of covariation among cluster sizes of 0.25. A two-tailed t-test was used with a significant level of 0.05 and the degrees of freedom based on the number of subjects.

Aim 3: We will use process-based costing to determine average costs for using the SPEEKO for Elderspeak feedback app, comparing costs relative to any difference determined for reductions in diminutive use in the immediate and delayed feedback groups.^{80,81}

D. Subject Criteria (See Vulnerable Populations appendix, if applicable):

1. Inclusion criteria: We will recruit CNAs who are age 18 or older, permanent employees, and fluent in English to participate. Descriptive information (age, sex, race, ethnicity, role, experience) will be used to identify CNA covariate factors predicting communication

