3. **AIM 3.** Evaluate app acceptability and costs. **Analysis:** Process-based costing to determine average costs for using the SPEEKO for Elderspeak feedback app, comparing costs relative to any difference determined for reductions in diminutive use in the immediate and delayed feedback groups.

B. Outcome:

1. **AIM 1 Expected Outcome:** The app will be readily used and acceptable to CNAs. Diminutive counts determined by the app will be correlated with psycholinguistic analysis, validating accuracy.
2. **AIM 2 Expected Outcome:** Staff who receive immediate app feedback (N= 30 in three NHs) will have greater elderspeak reduction after completing CHATO training compared to delayed feedback controls (N= 30 in three NHs).
3. **AIM 3 Expected Outcome:** Staff who use the app will find it acceptable and beneficial for their practice. Process-based costing will be used to determine costs for app use in NHs and other long-term service and support settings. Costs will be compared in relation to each group's outcomes.

C. Study results to participants: Audio recording feedback via the app will be provided either immediately after recording (treatment group) or at the end of the study (control group). Nursing homes will receive CHATO participation rate feedback.

D. Publication Plan: The PI will develop an appropriate plan for publication of research results based on the study aims and results.

VI. Bibliography / References / Literature Cited

1. Department of Health and Human Services. *National plan to address Alzheimer's disease: 2015 Update*. 2015.
2. Alzheimer's Association (2017). Alzheimer's Disease Facts and Figures.

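### Correlating app counts with coded counts is named as proof of accuracy, but correlation cannot see proportional miscounting; agreement measures, including positive predictive value, should take its place

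*Combined protocol and SAP*

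**What the plan says.** Sections I.A (Aim 1 hypothesis) and V.B, item 1 carry the same sentence: "Diminutive counts determined by the app will be correlated with psycholinguistic analysis, validating accuracy". No type of coefficient, threshold or interval is given.

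The methods text describes the check more loosely. Section II.C, Aim 1 sets "a diminutive accuracy testing benchmark of 80% or higher" and adds: "App outputs will be compared to data from transcription and psycholinguistic coding, using our established protocols, to validate app reliability for diminutive detection". For Aim 2, section II.B (Preliminary Effects Testing) says: "We will validate app accuracy by comparing app results to psycholinguistic coding". None of these names a statistic. Section V.A, item 1 lists only a usability scale as the Aim 1 analysis.

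The nearest thing to a definition of accuracy is in section II.B (Feasibility Testing), where the laboratory test of the detection model is reported as "a sensitivity (true positive rate) of 87.7% and a specificity (true negative rate) of 99.9" per cent.

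Two other passages matter. The app "identifies and tabulates diminutives, displaying a feedback infographic at the end of the session" (section II.B, iOS App), so its count is what the CNA sees. And "RAs will transcribe all recordings (for both groups) and will use brackets to code diminutives" (section II.B, Psycholinguistic Coding), with the coders blind to group and time point.

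**The concern.** Validity of the app is a stated objective of Aim 1, and comparing its accuracy with coding is a stated part of Aim 2. Correlation is the only statistic that the plan names for this comparison. It answers whether CNAs with higher coded counts also have higher app counts. It does not answer whether the app's count is right.

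Under-counting is the foreseeable error: the laboratory sensitivity of 87.7% already means that about 12% of terms are missed, and section II.B lists background noise and bandwidth as open issues for live use. Misses at a roughly constant rate leave a correlation almost untouched.

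At stake are the claim that the app is valid, the later decision to extend its functions if it is validated (section II.B), and the reading of a null Aim 2 result. If feedback had no effect, one would want to know whether the feedback itself was accurate.

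**Working it through.** The 80% is a chosen threshold, so there is no planned figure to reproduce. The inputs from the documents are five Aim 1 sessions, laboratory sensitivity (Se) 0.877 and specificity (Sp) 0.999, and 60 CNAs × 4 = 240 Aim 2 sessions. The documents give no diminutive counts and no share of diminutives among scored units; values for these below are assumptions.

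**1. Proportional miscounting.** If the app records k times the coded count N, then r = cov(N, kN) / [SD(N) × SD(kN)] = k·var(N) / [k·var(N)] = 1 for any k > 0. Take illustrative coded counts 4, 9, 15, 22, 40 and halve each:

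- Means are 18 and 9, variances 157.2 and 39.3, covariance 78.6.
- r = 78.6 / √(157.2 × 39.3) = 1.00.
- Total count ratio = 45/90 = 0.50.
- Lin's concordance coefficient = 2 × 78.6 / (157.2 + 39.3 + 9²) = 157.2 / 277.5 = 0.57.

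Doubling every count also gives r = 1.00 and concordance 0.57. Agreement measures show the fault; correlation does not.

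**2. Random misses.** In a simulation, session counts were assumed negative binomial (mean 20, size 1.5), each term was detected with probability 0.5, and there were no false alarms. The median r was 0.975 with 5 sessions (5th to 95th percentile 0.81 to 0.998) and 0.967 with 240 sessions treated as independent. More sessions do not cure the problem.

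**3. Precision with five sessions.** Fisher z for r = 0.9 is 1.472, with SE = 1/√(5 − 3) = 0.707. The 95% limits are tanh(1.472 ± 1.96 × 0.707) = 0.09 and 0.99.

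**4. What the 80% benchmark adds.** Section II.C uses the same term for the test as section II.B, which reports sensitivity and specificity.

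- If sensitivity is included, an app that detects half of the terms has Se = 0.50 < 0.80 and fails.
- Neither measure gives the share of flagged terms that are correct. That is PPV = Se·p / [Se·p + (1 − Sp)(1 − p)], where p is the share of diminutives among scored units.

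With the laboratory figures, and using app/coder count ratio = (TP + FP)/(TP + FN) = Se/PPV:

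| p (assumed) | PPV | Count ratio |
|---|---|---|
| 5% | 0.98 | 0.90 |
| 1% | 0.90 | 0.98 |
| 0.5% | 0.82 | 1.08 |
| 0.2% | 0.64 | 1.38 |
| 0.1% | 0.47 | 1.88 |

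Se and Sp both clear 80% in every row, yet the app ranges from under-counting by about a tenth to nearly doubling the count. At p = 1% the total looks almost right (0.98), although 12% of true terms are missed and 10% of flagged terms are false. The errors cancel in the total, so a count ratio alone is not enough either.

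**The case against.** The strongest reply is that the quoted sentence is a hypothesis and an expected outcome, not an analysis specification. The methods text says that app output will be compared with coding and sets a benchmark, and its shared term points to sensitivity and specificity. This largely stands. The plan does not rest on correlation alone, and its comparison wording leaves room for an agreement analysis. What it does not do is name one, and the only statistic it names is the one that cannot support the claim attached to it.

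A reader might infer that the plan would declare an app valid while it missed half of all diminutives. The documents do not support that: on the likely reading of the benchmark, such an app fails on sensitivity. What stays uncovered is false alarms, and the choice of measure remains unstated.

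A reader might also infer that the Aim 2 group comparison is biased by app error. That does not follow either. All recordings in both groups are transcribed and coded by blinded staff, so the comparison need not be affected if coder counts are the outcome.

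Finally, matching app flags to transcripts takes real work, because the app trims by voice activation and the recordings are later edited to remove names and other speakers. That is a fair cost, and it belongs in the decision.

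**Conclusion.** The point holds within limits. Correlation should not be the stated evidence of accuracy: it equals 1 under any constant proportional error, and with five sessions it is also very imprecise. The 80% benchmark probably protects against gross under-counting, but that rests on inferring its meaning from section II.B, and even then it says nothing about the share of flagged terms that are false. The consequence is confined to the app validity claim and the interpretation of the feedback. This is an inexpensive improvement that should be made; it is not a flaw in the Aim 2 design.

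The algebra in steps 1 and 4 needs no assumption. The simulated correlations and the PPV range depend on assumed counts and an assumed diminutive share; they illustrate the problem and do not predict this app's performance.

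**What to change.** 1. In section I.A (Aim 1 hypothesis) and section V.B, item 1, replace correlation as the evidence of accuracy with agreement against the coded transcripts: term-level sensitivity and PPV, plus the app/coder count ratio or mean difference per session. Correlation can stay as a descriptive figure. Sensitivity and PPV have the further merit of not needing a definition of a true negative.
2. In section II.C, state that the 80% applies to sensitivity, or to whichever measure the sponsor intends. Say that it is compared with a point estimate that is imprecise with five CNAs.
3. Use the same measures for the Aim 2 accuracy comparison in section II.B, where about 240 coded sessions will be available.
4. Settle these choices before app and coder results are compared.

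The cost: the terms that the app flags in each session must be saved and matched to the coded transcripts, and the validity standard becomes somewhat stricter. No new recordings or coding are needed. The Aim 1 estimates remain imprecise whichever measure is used.

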APPENDIX I: VULNERABLE POPULATIONS

- I. Cognitively or decisionally impaired individuals:** This study will include **NH staff who work with a vulnerable population of older adults including persons with dementia**. Of importance to these populations is the protection of privacy and confidentiality of materials that might be used for performance evaluations or released to unauthorized parties. This is a minimal risk study because protections and protocols limit the probability and magnitude of harm or discomfort from participation. Harm and discomfort is not greater than that ordinarily encountered in daily life or during the performance of routine physical or psychological examinations or tests.
- II. Children:** N/A
- III. Pregnant women:** N/A
- IV. Prisoners:** N/A
- V. Students and/or Employees:** N/A
